## **9.4 Type and Duration of Follow-up of Subjects after Adverse Events**

All AEs and SAEs will be followed from the time of study treatment through resolution even if this extends beyond the study reporting period (i.e., the Month 1 visit). Resolution of an AE/SAE is defined as the return to pretreatment status or stabilization of the condition with the expectation that it will remain chronic.

Follow-up procedures, evaluations, and outcomes will be recorded on the appropriate data collection form.

## **9.5 Halting Rules**

Further enrollment will be halted for DSMB review if any of the following are reported:

- If one or more subjects experience an SAE judged by an investigator to be related to the study drug
- An overall pattern of clinical events that the DMID Medical Monitor or DSMB consider associated with the study drug and that may appear minor in terms of individual events, but that may collectively represent a serious potential concern for safety

If any of the halting rules are met, the study will not continue with the remaining enrollments or study treatments without a review by and recommendation from the DSMB to proceed.

DMID retains the authority to suspend additional enrollment and administration of the study drug during the entire study, as applicable.

---

## 9.6 Safety Oversight (ISM plus DSMB)

An ISM at each clinical research site will oversee the safety of research subjects at that site and will provide independent written evaluation of SAEs and related Grade 3 AEs to the PI, DMID Clinical Project Manager, and DMID Medical Monitor. The ISM will serve as an independent consultant for the site PI on subject-related issues. The ISM will communicate with the site PI and study PIs to resolve any issues.

Safety oversight will be conducted by a DSMB that is an independent group of experts that monitors subject safety and advises DMID. The DSMB members will be separate and independent of study personnel participating in this trial and should not have scientific, financial, or other conflict of interest related to the study. The DSMB will consist of members with appropriate expertise to contribute to the interpretation of the data from this trial.

The DSMB will review safety and enrollment data when half of the study subjects have been enrolled and observed for SAEs through the Month 1 Visit.

The DSMB will review study progress and subject clinical and safety data at the following time points:

- At least annually after the first subject is enrolled.
- Ad hoc when a halting rule is met, for immediate concerns regarding observations during the study, or as needed.
- During a final closeout meeting, held at the end of the study after the database is locked to review cumulative study data prior to finalizing the Clinical Study Report (CSR).

The DSMB will operate under the rules of a DMID-approved charter that will be written at the organizational meeting of the DSMB. As an outcome of each review/meeting, the DSMB will make a recommendation as to the advisability of proceeding with study administrations (as applicable), and to continue, modify, or terminate the study.

DMID or the DSMB chair may convene the DSMB on an ad hoc basis according to protocol criteria or if there are immediate concerns regarding observations during the study. The DMID Medical Monitor is empowered to stop enrollment and study treatment if SAEs that meet the halting criteria are reported. The DMID Medical Monitor will be responsible for reviewing SAEs in real time. The DSMB will review SAEs on a regular basis and *ad hoc* during the study.

## **10 CLINICAL MONITORING**

### **10.1 Site Monitoring Plan**

DMID, the sponsoring agency, or its designee will conduct site monitoring visits as detailed in the clinical monitoring plan and in accordance with DMID policies. Site monitoring is conducted to ensure that the human subject protections, study and laboratory procedures, study intervention administration, and data collection processes are of high quality and meet sponsor and ICH/GCP guidelines and applicable regulations and that the study is conducted in accordance with the protocol, protocol-specific manual of procedures, and applicable sponsor SOPs. Monitoring visits will include, but are not limited to, inspection of study facilities; review of regulatory files, accountability records, eCRFs, ICFs, printouts of medical and laboratory reports from the electronic medical records (EMR) system; and review of protocol and GCP compliance. Site monitors will have access to the study site, study personnel, and all study documentation according to the DMID-approved site monitoring plan. Study monitors will meet with PIs to discuss any problems and actions to be taken and document visit findings and discussions.

Site visits will be made at standard intervals as defined by DMID and may be made more frequently as directed by DMID.

---

## 11 STATISTICAL CONSIDERATIONS

### 11.1 Study Hypotheses

The primary objective of the study is to compare the serological response to therapy in subjects with early (primary, secondary, or early latent) syphilis treated with BPG 2.4 MU once or weekly for three successive weeks. In particular, the objective is to demonstrate noninferiority of the one-dose regimen compared to the three-dose regimen and to also assess noninferiority within the HIV status subgroups (HIV-infected and HIV-uninfected subjects). See Section 11.4.4 for the definition of serological response.

The null hypothesis for the primary objective is that the difference in serological response rate between the three-dose and one-dose groups is at least 10%, and the alternative hypothesis is that the difference in response rates is less than 10%. The null and alternative hypotheses for the secondary HIV status subgroup objective are defined similarly.

Note that tests will be performed and p-values will be reported for secondary analyses for informational purposes and not to make definitive claims. The study is intended and designed to formally test the primary hypothesis only, and so no corrections for multiplicity are planned.

### 11.2 Sample Size Considerations

Sample size calculations were performed using PASS 2008 and SAS 9.4. The following parameters were used for determining the required sample size for the primary objective:

- 1:1 allocation ratio between one-dose and three-dose arms
- Test the difference in response rate between the one-dose and three-dose arms (Farrington-Manning test, unadjusted for HIV status)
- Null hypothesis response rate in one-dose arm: 0.688
- Null hypothesis response rate in three-dose arm: 0.788
- Alternative hypothesis response rate in both arms: 0.788
- One-sided 0.05 alpha level

To achieve 80% power for the primary noninferiority comparison, 420 evaluable subjects (210 in each treatment arm) are needed. It is assumed that 25% of subjects will be ineligible for the primary analysis, and so 560 enrolled subjects are needed to reach the target of 420 evaluable subjects.

The study is not powered to assess the secondary noninferiority comparisons in the HIV status subgroups. As an illustration, power calculations were performed to assess the power available for these subgroup analyses using a sample size of 420. The following parameters were used for the calculations:

- Test the difference in response rate between the one-dose and three-dose arms within each HIV status stratum.
- Null hypothesis response rate in one-dose arm: 0.738 (HIV-infected); 0.638 (HIV-uninfected)
- Null hypothesis response rate in three-dose arm: 0.838 (HIV-infected); 0.738 (HIV-uninfected)
- Alternative hypothesis response rate in both arms: 0.838 (HIV-infected); 0.738 (HIV-uninfected)
- One-sided 0.05 alpha level
- 280 evaluable subjects in the HIV-infected stratum (140 in one-dose arm, 140 in three-dose arm).
- 140 evaluable subjects in the HIV-uninfected stratum (70 in one-dose arm, 70 in three-dose arm).

The HIV-infected noninferiority comparison has 72% power, and the HIV-uninfected noninferiority comparison has 38% power.

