## 5.3 Treatment Assignment Procedures

### 5.3.1 Randomization Procedures

Enrollment of subjects will be done online using the enrollment module of Emmes Advantage eClinical®. Subjects will be randomized at a 1:1 ratio to receive one of the two BPG treatments after informed consent is obtained and their eligibility is confirmed.

The study will use a stratified, permuted block-randomization scheme. Permuted block randomization is used to avoid the potential for serious imbalance in the number of subjects assigned to each group, an imbalance that can occur in the simple randomization procedures. Stratification will be by study site. While HIV status may not be known at the time of randomization, subjects will be classified as HIV-infected or HIV-uninfected to assess the secondary HIV status subgroup objective, and randomization will be limited as follows:

- If 280 subjects who were HIV-infected at baseline are confirmed evaluable, additional subjects who are known to be HIV-infected will not be allowed to enroll thereafter, while HIV-uninfected subjects and subjects of unknown HIV status may continue to enroll.
- If 140 subjects who were HIV-uninfected at baseline are confirmed evaluable, only subjects who are known to be HIV-infected will be allowed to enroll thereafter.

The list of randomized treatment assignments will be prepared by statisticians at Emmes and included in the enrollment module of its Internet Data Entry System (IDES). IDES will assign each subject a treatment code from the list after demographic and eligibility data have been entered.

Instructions for use of the enrollment module are included in the IDES User's Guide. Manual back-up randomization procedures are provided in the Manual of Procedures (MOP) for use in case a site temporarily loses access to the Internet or the online enrollment system is unavailable.

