### 11.4.4 Efficacy Analysis Plan

#### 11.4.4.1 Primary Efficacy Analysis

For the primary analysis, serological response to therapy by Month 6 will be defined as follows:

- 4-fold or greater decline in RPR titer by Month 6 compared to baseline, OR
- RPR-negative by Month 6 (i.e., seroreversion).

For the primary analysis, subjects who do not meet either of the above criteria by Month 6 will be classified as not experiencing serological response. If a subject has an observed serological response prior to meeting one of the Evaluable analysis population exclusion criteria, the subject will be included in the analyses as a responder. For subjects who have received BPG through the study and subsequently require retreatment for syphilis infection (i.e., per the local clinic's standard protocols), data collected following retreatment will not be used for analyses. Exploratory analyses of the primary outcome will consider alternative classifications of subjects (see Section 11.4.4.2).

For the comparison of efficacy of one dose versus three doses of BPG 2.4 MU, the number and proportion of subjects with serological response will be summarized overall and by treatment.

The point estimates for the treatment-specific proportions and difference in proportions as well as corresponding 95% confidence intervals will be reported. A hypothesis test will be conducted using the Farrington-Manning test at the 5% one-sided level of significance to formally compare the treatment arms. The primary analysis will be performed in the ITT analysis population and repeated as a secondary analysis in the mITT and the Evaluable analysis populations.

As the ITT analyses will include subjects who may not have adequate serological data to determine their response status for any reason, the response will need to be imputed. Multiple methods for imputation will be explored (e.g., Last Observation Carried Forward); details will be provided in the Statistical Analysis Plan.

As a secondary corroborative analysis, the Cochran-Mantel-Haenszel Chi-square test will be used to compare the two treatment arms with respect to response rate across HIV status subgroups (HIV-infected, HIV-uninfected). The Breslow-Day test for the homogeneity of odds ratios will be used to determine if the difference between the two treatment groups with respect to response rates varies by HIV status.

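### The primary noninferiority test is valid but unadjusted: it leaves out site, baseline RPR titer and syphilis stage, so a cheap gain in precision is missed

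*Protocol*

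**What the plan says.** - **Hypothesis (section 11.1).** Under the null, the "difference in serological response rate between the three-dose and one-dose groups is at least 10" percent. The effect measure is therefore a risk difference with a 10-point margin.
- **Sample size (section 11.2).** The basis is a "Farrington-Manning test, unadjusted for HIV status", with "1:1 allocation ratio between one-dose and three-dose arms", "One-sided 0.05 alpha level", "Null hypothesis response rate in one-dose arm: 0.688" and "Alternative hypothesis response rate in both arms: 0.788". This gives 420 evaluable subjects for 80% power and 560 enrolled.
- **Primary analysis (section 11.4.4.1).** "A hypothesis test will be conducted using the Farrington-Manning test at the 5% one-sided level of significance to formally compare the treatment arms". It is done in the ITT population, with missing responses imputed. No covariate is named.
- **Randomization (section 5.3.1).** "Stratification will be by study site". HIV status may be unknown at that moment.
- **HIV status.** It enters only secondary analyses: the Cochran-Mantel-Haenszel and Breslow-Day tests (section 11.4.4.1) and separate tests within each HIV subgroup (section 11.4.4.2).
- **Left to the SAP.** Section 11.4 leaves analysis details to the SAP, and section 11.4.4.3 leaves exploratory and sensitivity analyses to it. The primary test itself is fixed in the protocol.

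**The concern.** Three baseline variables that could sharpen the primary comparison do not enter it.

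- **Site** is built into the allocation but not into the variance. When response differs between sites, the unadjusted standard error is then a little too large.
- **Baseline RPR titer** is part of the endpoint. Response means a four-fold fall (two dilutions) or seroreversion. Inclusion criterion 4 sets no minimum titer, since a newly reactive test is enough. Taking 1:1 as the lowest reactive reading, a subject entering at 1:1 or 1:2 can respond only by seroreversion, while a subject entering at 1:64 has several dilutions of room.
- **Stage** is established at eligibility.

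Titer and stage are not stratification factors, so neither the design nor the primary estimate deals with a chance imbalance between arms. With power close to 80% at 420 evaluable subjects, what is at stake is some precision and protection against such an imbalance. Validity is not at stake.

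**Working it through.** **Inputs from the protocol.** Response 0.788 in both arms under the alternative, margin 0.10, one-sided 0.05 and 210 per arm (sections 11.1 and 11.2). Response by HIV status is 0.838 and 0.738, with 280 and 140 evaluable subjects (section 11.2).

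**Assumed, because the protocol gives no figure.** R-squared, the share of outcome variance explained by titer, stage and site.

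**Step 1: reproduce 420.** The restricted null rates for the Farrington-Manning test are 0.7297 and 0.8297.
- Null SD term: s0 = sqrt(0.7297×0.2703 + 0.8297×0.1703) = 0.5818.
- Alternative SD term: s1 = sqrt(2×0.788×0.212) = 0.5780.
- n per arm = ((1.645×s0 + 0.842×s1)/0.10)² = 208.4, so N = 418 against the stated 420.
- Power at 210 per arm = Φ((√210×0.10 − 1.645×s0)/s1) = 80.3%. Exact enumeration gives 80.4%.
- Exact one-sided size at 0.688 versus 0.788 is 0.0505.

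The plan's figure holds, and the test is sound as it stands.

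**Step 2: HIV status, from the protocol's own rates.**
- Mean rate with the 2:1 split: (2×0.838 + 0.738)/3 = 0.805.
- Between-group variance: (2/3)(1/3)(0.10)² = 0.0022. Total variance: 0.1572. R-squared = 0.014.
- Power goes from 80.3% to 80.8%, and N for 80% power from 418 to 412.
- A simulation of 10,000 trials with a simple risk-difference test at these rates gave 82.8% unadjusted and 83.1% stratified by HIV status. The two are within simulation error.

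**Step 3: titer and stage, over an assumed range.** Adjustment multiplies the variance by (1 − R²), so power = Φ((√(210/(1−R²))×0.10 − 1.645×s0)/s1).

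| Assumed R² | Power at 420 evaluable | N for 80% power |
|---|---|---|
| 0 | 80.3% | 418 |
| 2% | 81.0% | 410 |
| 5% | 82.0% | 396 |
| 10% | 83.8% | 376 |
| 15% | 85.6% | 356 |

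Simulations with three assumed prognostic strata agree. Power went from 80.6% to 81.9% at R² = 5.6%, and from 80.4% to 83.8% at R² = 11.1%. Estimated sizes at these two settings were 0.048 to 0.049 for both tests.

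**Step 4: site, with an assumed between-site SD of response of 0.03 to 0.10.**
- R² = SD²/(0.788×0.212) = 0.005 to 0.060.
- True size of the unadjusted test = 1 − Φ(1.645/√(1−R²)) = 0.0495 to 0.045.

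The departure from 0.05 is on the conservative side.

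**Step 5: the primary population.** Steps 1 to 4 use 420 evaluable subjects, but the primary analysis is ITT, about 280 per arm.
- If the imputed response rate stays at 0.788, unadjusted power is about 89%.
- If, as an extreme, the 25% non-evaluable all count as non-responders, the rate is 0.75×0.788 = 0.591. The SE is sqrt(2×0.591×0.409/280) = 0.0416, and power is Φ(0.10/0.0416 − 1.645), about 78%.

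Between these two cases, imputation moves power by about 11 points. That is more than adjustment does anywhere in the table.

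**The case against.** The strongest reply is that nothing here is wrong. The test addresses the stated hypothesis on the stated scale, the sample-size and analysis sections agree, the size is right and the power target is met. All of that stands. A reader might infer that leaving out site inflates the type I error, or that the trial is underpowered. The document supports neither: the site effect is conservative, and 420 reproduces.

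The second reply is that the benefit is unproven. This also stands. The one covariate whose effect the protocol quantifies, HIV status, is worth about half a power point. Figures for titer and stage rest on an assumed R-squared, and none of them describes the ITT analysis directly. At the protocol's 2:1 HIV mix the rate is 0.805 rather than 0.788, and unadjusted power at 420 is already about 82.6%.

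Third, adjustment is not costless. The ITT population may include subjects without a known HIV status or an adequate baseline titer, because section 11.4.1 requires those only for the Evaluable population. Small sites may also need pooling.

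Fourth, a reader might infer that HIV status is ignored altogether. It is not, since several secondary analyses use it. They do not fill the gap, however. The Cochran-Mantel-Haenszel test uses HIV status alone and tests equality on the odds-ratio scale, not the 10-point margin. Nor can the matter be left wholly to the SAP: an adjusted sensitivity analysis could sit there, but an adjusted primary test would contradict section 11.4.4.1.

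**Conclusion.** The point holds as a cheap improvement to a valid plan. The primary test leaves out the stratification factor, a baseline value that the endpoint definition ties to response, and stage. A standardized risk difference could use all three without changing the effect measure or the margin.

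The likely size is modest. Power at 420 evaluable subjects rises from 80.3% to about 81.0% to 85.6% if R-squared lies between 2% and 15%, which is an assumption. HIV status contributes about 0.5 points. The absolute power of the ITT analysis differs and depends on the imputation, so these figures should not be read as the trial's actual gain.

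**What to change.** Before treatment-arm data are analysed, amend section 11.4.4.1 as follows.

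- **Primary ITT estimate and test.** Use a covariate-adjusted risk difference from a logistic model standardized over the trial population, with a robust variance. Covariates are log2 baseline RPR titer, stage, site and, optionally, HIV status.
- **Decision rule.** Compare the one-sided 95% bound with the same 10-point margin.
- **Site.** Prespecify how small sites are pooled.
- **Missing baseline covariates.** Prespecify a simple rule, such as a missing category or baseline imputation that ignores arm.
- **Missing responses.** State how the adjusted estimate is combined with the planned imputation of response.
- **Sensitivity analysis.** Keep the unadjusted Farrington-Manning test in this role.

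The sample size in section 11.2 can stay as it is, with a sentence saying that it takes no credit for adjustment. The cost is protocol and SAP wording, some programming and the two rules for pooling and missing covariates. No new data are needed.

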## **11.3 Planned Interim Analyses**

### **11.3.1 Safety Review**

The study will be monitored to determine if any of the safety halting rules described in Section 9.5 are met. The DSMB will also review study progress and subject safety data at specified times during the study and hold a study closeout meeting, as defined in the DSMB Charter.

### **11.3.2 Immunogenicity or Efficacy Review**

There are no planned interim analyses of efficacy data.

---

## 11.4 Final Analysis Plan

A separate statistical analysis plan document will be generated that will contain the details of the analyses. This section outlines the major components of the analyses.

### 11.4.1 Analysis Populations

Intent-to-Treat (ITT) Population: This analysis population includes all randomized subjects.

Modified Intent-to-Treat (mITT) Population: This analysis population includes all randomized subjects who are eligible at the baseline visit and whose TPPA result is positive at the baseline visit and/or at Visit 5 (Month 3), if repeat testing was performed.

Safety Population: This analysis population includes all randomized subjects who received at least one dose of study treatment.

Evaluable Population: This analysis population includes all randomized subjects who are eligible at the baseline visit, have a known HIV status determined at or before the baseline visit, have positive TPPA results at the baseline visit and/or Visit 5 (Month 3) (if repeat testing was performed), received all assigned doses of BPG, have adequate RPR titer data available at baseline and applicable follow-up visit(s), and (for HIV-uninfected subjects only) HIV-uninfected status persists through applicable follow-up visit(s).

If a subject receives antibiotic(s) active against *T. pallidum* for reasons other than syphilis between enrollment and the applicable follow-up visit(s), the subject will be included in ITT analyses but excluded from Evaluable analyses. If a subject receives antibiotic(s) active against *T. pallidum* between enrollment and the applicable follow-up visit(s) due to local RPR testing results, the subject will be included in all analyses.

A blinded case review committee will review subjects' data to determine if treatment with drug(s) known to be active against *T. pallidum* for reasons other than syphilis infection excludes the subject from the Evaluable analysis population.

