## 4 STUDY DESIGN

This is a Phase 4, open-label, multicenter trial to evaluate the efficacy of a single injected dose of BPG 2.4 MU (Arm 1) compared to three successive weekly injected doses of BPG 2.4 MU (Arm 2) for treatment of early syphilis in HIV-infected and HIV-uninfected subjects. Subjects will be aged 18 years or older with untreated early syphilis (primary, secondary, or early latent as defined in prior syphilis treatment trials of the Sexually Transmitted Infections Clinical Trials Group (STI CTG)). The study will be conducted at 10 sites in the US and will enroll approximately 560 subjects to achieve 420 evaluable.

The study will involve a screening/enrollment visit and seven scheduled follow-up visits (Weeks 1 and 2, and Months 1, 3, 6, 9, and 12) over a 12-month period. At the enrollment visit, after providing informed consent, all subjects will undergo a brief sexual and medical history and a directed physical examination; all women of childbearing potential will have a urine or serum pregnancy test performed as part of qualification for study participation; all subjects will undergo phlebotomy for serological testing for syphilis and HIV according to the study and clinic protocols. All subjects who have not been tested for chlamydia and gonorrhea since last sexual activity and all subjects who have been sexually active in the past 14 days will have specimens collected for chlamydia and gonorrhea testing. Subjects will have specimens collected for other STI testing as indicated by local standard of care and subject history. All eligible subjects will be randomized to Arm 1 or Arm 2 and will receive an injected dose of BPG 2.4 MU.

Study personnel will attempt to contact subjects approximately 24 hours after Visit 1 to assess for symptoms of a Jarisch-Herxheimer reaction as described in Section 8.1. At the second and third visits (Weeks 1 and 2 of follow-up), subjects randomized to Arm 2 will receive injected doses of BPG 2.4 MU.

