### **7.2.2 Visit 3 – Week 2 (6 to 12 days after Visit 2)**

- Subject will be evaluated for resolution of any clinical signs of infection.
- Medical history will be reviewed (including review of interval medical records and local laboratory results, if available) and updated as appropriate. If available in the medical record, the most recent viral load result since enrollment should be recorded. If the local laboratory results indicate a need for retreatment for syphilis infection, the subject will receive treatment according to the local clinic's standard protocols and will be withdrawn from the study per protocol Section 5.3.3.
- Interim sexual history since the last study visit will be collected. Specimens will be collected at sites of exposure for STI screening/diagnosis as indicated by local standard of care and subject history.
- A urine pregnancy test will be performed on all subjects of childbearing potential.
- All concomitant medications taken since the last study visit will be recorded on the appropriate data collection form. Previously recorded medications will be updated as appropriate.
- A targeted physical examination will be performed by a qualified study clinician (including vital signs: temperature, heart rate, respiration rate, and blood pressure; and genital, rectal, oral, skin, and lymph node examinations).
- Blood will be collected for follow-up RPR tests and storage.

- 
- Arm 2 only: third dose of BPG will be administered, and the subject will be observed per clinic SOP.
  - Study personnel will discuss with subjects and assess and record all AEs/SAEs (including solicited reactogenicity AEs and other unsolicited AEs).
  - Contact information will be reviewed, and the Month 1 visit will be scheduled.

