 At Visit 1, record concomitant medications taken in the last 30 days before initiating BPG. At subsequent visits, record all concomitant medications taken since the last visit and update previously recorded medications as appropriate.

 Collect for subjects with known HIV infection whose medical records do not include a CD4 count in the past 30 days; at Visit 4, this is only applicable to subjects newly found to have HIV infection from Visit 1 to Visit 4 (inclusive).

 Perform for subjects who do not have a previously documented positive HIV test result using locally available tests (e.g., nucleic acid tests (NATs), antibody/antigen tests).

 At Visit 1, collect specimens at sites of exposure for screening/diagnosis of chlamydia and gonorrhea for all subjects who have not been tested since last sexual activity and for all subjects who have been sexually active in the past 14 days and for other STIs as indicated by local standard of care and subject history. At subsequent visits, collect specimens at sites of

exposure for STI testing per local standard of care and subject history.

It is optional to swab subject's oral cavity and lesions, if lesions are present. See Section 8.2.2.

 At Visit 1, administer BPG to all subjects. At Visits 2 and 3, administer BPG to subjects in Arm 2 only.

At Visit 1, collect contact information. At subsequent visits, review contact information and update if needed.

 Distribute checklist at Visit 1. Subject refers to completed checklist during Jarisch-Herxheimer assessment; see Sections 7 and 8.1.

Assess per protocol Section 8.1. If subject is not reached, assess at Visit 2.

 Assess and record all AEs/SAEs (including solicited reactogenicity AEs and other unsolicited AEs).

 At Unscheduled Visits, any of the specified evaluations that are relevant to the subject may be performed at the discretion of the site PI.

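### The Evaluable dose criterion selects on early return in Arm 2 only, on top of eligibility and follow-up titer criteria common to both arms.

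*Protocol*

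**What the plan says.** Section 11.4.1 lists the Evaluable criteria. Those common to both arms are baseline eligibility, known HIV status, a positive TPPA, and adequate RPR data at baseline and the relevant follow-up visits. Subjects in either arm who receive certain antibiotics for reasons other than syphilis are excluded. The definition also requires that the subject "received all assigned doses of BPG".

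What that asks of each arm follows from the schedule. Appendix A states: "At Visit 1, administer BPG to all subjects. At Visits 2 and 3, administer BPG to subjects in Arm 2 only". Section 7.2.2 agrees: "Arm 2 only: third dose of BPG will be administered". The visits themselves are not specific to an arm. Section 4 gives every subject "seven scheduled follow-up visits (Weeks 1 and 2, and Months 1, 3, 6, 9, and 12) over a 12-month period", and sections 7.2.1 and 7.2.2 have blood drawn for RPR at Weeks 1 and 2 without regard to arm.

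Two rules in section 11.4.4.1 bear on the consequence. On the role of the Evaluable set: "The primary analysis will be performed in the ITT analysis population and repeated as a secondary analysis", the repeat being in mITT and Evaluable. On early responders: "If a subject has an observed serological response prior to meeting one of the Evaluable analysis population exclusion criteria", that subject is retained and counted as a responder.

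**The concern.** The dose criterion is applied after randomization and acts differently by arm. Take a subject who misses Week 1 or Week 2 but is seen at Month 6. In Arm 1 that subject remains Evaluable. In Arm 2 the same behavior normally leads to exclusion. The Arm 2 group is filtered on early return and the Arm 1 group is not. Any association between early return and serological response, for example through reinfection risk or engagement in care, then appears as a difference between regimens.

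Section 5.3.3 adds to this. It allows discontinuation from further dosing in Arm 2 for several reasons, among them missed visits and investigator's discretion, and Arm 1 has no counterpart because it has no further doses.

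The primary test is not at stake, but the Evaluable result is more than decoration. The 420-subject target (section 11.2) and the HIV enrollment limits (section 5.3.1) are counted in evaluable subjects. The secondary efficacy analyses use only ITT and Evaluable (section 11.4.4.2). ITT needs imputed responses where titers are inadequate, so the Evaluable analysis is the main check that does not rely on imputation.

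**Working it through.** **The plan's own figures.** Inputs from sections 11.1 and 11.2: response 0.788 in both arms, margin 0.10, one-sided alpha 0.05, 210 evaluable per arm. Farrington-Manning power at 210 per arm is 80.3%, and 209 per arm reach 80%. 420/(1 − 0.25) = 560 enrolled. The sample size reproduces and is not in dispute.

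**Who creates the asymmetry.**

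| Subject | Arm 1 | Arm 2 |
|---|---|---|
| Attends Visits 2 and 3, adequate titers | in | in |
| Misses Visit 2 or 3, adequate titers | in | out, unless kept as an earlier responder |
| Drops out early, no adequate titers | out | out |

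Only the middle row differs.

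**Bias with assumed inputs.** The protocol gives one overall loss figure (25%) and none by arm or visit, so the following are assumptions:
- q, the share of each arm that would miss Visit 2 or 3: 10% to 15%.
- s, the share of those who still supply Month 6 titers: 50% to 90%, against 90% of the others.
- Response difference between returners and non-returners: 15 points.

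Share of non-returners in Arm 1 Evaluable = q·s / (q·s + (1 − q)·0.9). Bias = share × 0.15.

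If returners respond better, Arm 1 looks worse. SE = √(2 × 0.788 × 0.212/210) = 0.0399 and power ≈ Φ((0.10 − bias)/0.0399 − 1.645). With no bias this gives 80.6%.

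If returners respond worse, Arm 1 looks better. With true rates of 0.688 and 0.788, SE = √((0.688 × 0.312 + 0.788 × 0.212)/210) = 0.0426 and type I error ≈ Φ(bias/0.0426 − 1.645). With no bias this gives 5%.

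| q, s | Share | Bias (points) | Power if returners respond better | Type I error if they respond worse |
|---|---|---|---|---|
| 0.10, 0.5 | 0.050/0.860 = 5.8% | 0.87 | 74% | 7.5% |
| 0.15, 0.5 | 0.075/0.840 = 8.9% | 1.34 | 70% | 9.2% |
| 0.15, 0.9 | 0.135/0.900 = 15.0% | 2.25 | 62% | 13.2% |

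These hold 210 per arm fixed.

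**Wider range.** Let non-returners be 5% to 20% of otherwise evaluable subjects, let the response difference be 10 to 20 points, and shrink Arm 2 accordingly. The bias is then 0.5 to 4.0 points. Farrington-Manning power falls to between 76% and 44% in one direction. In the other, type I error rises to between 6% and 22%. With no response difference there is no bias, and power is 77% to 80% from lost numbers alone.

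**Early-responder rule.** If a share e of Arm 2 dose-missers had responded before the miss, the Arm 2 rate becomes ((1 − q)·0.788 + q·e)/((1 − q) + q·e). Here q is their share of otherwise evaluable subjects, and response is taken as unrelated to return. With e of 10% to 30% (assumed), this adds 0.2 to 0.7 points in favor of Arm 2 at q = 10%, and 0.4 to 1.1 at q = 15%. The effect should be limited: a subject who misses Visit 2 will usually have no follow-up titer before the miss, so the rule mainly reaches those who attended Visit 2 and missed Visit 3.

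**The case against.** The strongest objection is that this is an ordinary per-protocol-type criterion in a secondary analysis. ITT is primary, mITT has no dose condition, and section 11.1 says that secondary tests are informational. Sections 11.4 and 11.4.4.3 leave further sensitivity analyses to a statistical analysis plan that is not at hand. Section 11.4.4.2 already compares dose compliance by arm. Inclusion criterion 7 and exclusion criterion 6 aim to limit non-return. Section 11.4.1 sets no visit window for doses, unlike the compliance definition in section 6.4, so a late Arm 2 dose may still qualify. All of this stands and limits the consequence. It does not remove the asymmetry, which the protocol's own definition fixes.

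The size is also open to challenge. No input to the bias calculation comes from the protocol. The 62% figure needs early non-returners to supply Month 6 titers as often as everyone else yet respond 15 points worse, which is a strained pairing. That stands too: the figures are illustrations.

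A reader might infer that Arm 1 is unselected, or that nothing comparable is asked of it. The text does not support that. Both arms must return for adequate titers and both lose subjects under the common criteria.

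A reader might also expect a set matched on attendance to separate selection from a dose effect. It cannot. The trial is open label, Arm 1 subjects have no dose to collect at Visits 2 and 3, and attendance may depend on arm. Arm 2 subjects can also attend and not be dosed, for example after an adverse event (section 5.3.3) or a pregnancy (section 9.3.3).

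**Conclusion.** The point holds in a limited form. The Evaluable definition conditions on early return in Arm 2 only, over and above criteria shared by both arms. The affected subjects are those who miss a Week 1 or Week 2 dose but still supply adequate titers, less any retained as earlier responders. The direction of bias is unknown, and the bias is zero if early return is unrelated to response. With 10% to 15% non-returners and a 15-point response difference, both assumed, it is about 1 to 2 points of the 10-point margin. In this secondary analysis that lowers power to between 74% and 62%, or raises one-sided type I error to between about 7% and 13%, depending on direction. The primary ITT test, its sample size and the mITT analysis are not called into question. A supporting analysis is worth adding because the Evaluable result will be read as the main check on an ITT result that uses imputation.

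**What to change.** Keep ITT as primary and keep the current Evaluable set. In section 11.4.1 add a sensitivity Evaluable set: the present criteria plus attendance at Visits 2 and 3 required in both arms. Run the same Farrington-Manning noninferiority analysis in it. Report the number excluded from the Evaluable population by arm and by reason, and state how many Arm 2 dose-missers were kept under the early-responder rule.

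Fix the interpretation in advance. Agreement between the two sets is supportive. Disagreement is a sign that selection may contribute, and is not proof, because the added set is itself selected after randomization.

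The cost is one more analysis set, built from visit data already collected. It loses some Arm 1 subjects. Dropping 9% leaves about 191 against 210: SE = √(0.788 × 0.212 × (1/191 + 1/210)) = 0.0409, power about 79%. Dropping 15% leaves about 178.5: SE = 0.0416, power about 78%. No treatment, visit or primary analysis changes.
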